13.2 Blood Biomarkers gene expression analyses and DNA sequencing

Blood sampling for biomarkers (around 10mL) will be performed at the inclusion (V1) and at 6-month (V3), 12-month (V5) and 15-month (V6) visits for a total of 15 ml each time.

Five potential blood biomarkers have been selected (tryptophan, alanin, serotonin, T4 and free cholesterol), first through a pilot study exploring the differences in the expression of potential biochemical markers in Transgenic PMP22 rats versus Wild Type Sprague Dawley rats. The phase II conducted in humans provided confirmation of the interest of these biomarkers, particularly tryptophan, alanine and free cholesterol. Moreover other markers could be assessed for quantification studies, and thus identified later after the accomplishment of this clinical trial.

An additional blood sample (5mL) will be drawn at the inclusion visit only to collect leucocytes in order to realize DNA sequencing for research purposes.

Complete information on blood sampling, conditions of preparation and storage (-80°C) as well as shipment details for these samples will be supplied in a separate technical brochure.

13.3 Skin biopsy (optional ancillary sub-study)

Some investigating site will perform skin biopsies. A specific processing protocol will be provided.

Skin biopsy is a minimally invasive procedure that is used mainly in the evaluation of non-myelinated nerve fibres in sensory neuropathies. Recent data suggested that skin biopsy may replace, under certain circumstances, the more invasive sural nerve biopsy in the morphological and molecular evaluation of inherited and other demyelinating neuropathies (Li, Bai *et al.*, 2005; Katona, Wu *et al.*, 2009; Saporta, Katona *et al.*, 2009).

A skin biopsy consisting in one small punch biopsy (3 mm of diameter) at the lateral calf 10 cm above the lateral malleolus will be performed before treatment at baseline (V1) and after treatment (V6) to all patients randomized in the site that are engaged in this sub-study. This will allow to assess mRNA levels of PMP22 and other putative candidates biomarkers as exploratory pharmacodynamic endpoints of the present study. Complete information on sampling, conditions of preparation and storage as well as shipment details and laboratory contact details will be supplied in a separate technical brochure.

13.4 Leg MRI (optional ancillary sub-study)

Some investigating sites will participate in an optional ancillary sub-study leg MRI for research purpose on potential new imaging biomarkers. Legs MRI will be conducted at Baseline and the end of the study. A specific processing protocol will be provided separately to ensure the standardisation of the MRI acquisition across all sites, and centralized reading will be organized.

14. STATISTICAL CONSIDERATIONS

14.1 Analysis sets

The **Full Analysis Set (FAS)** will be constituted by all the randomized patients.

The **Per-Protocol (PP)** population will include all the patients of the FAS without major protocol violation during the course of the study.

All the efficacy analyses will be conducted on the FAS population and reproduced on the PP population for sensitivity purposes. The safety analyses will be conducted on the FAS, given that all randomized patients will receive at least one dose of treatment.

14.2 Primary efficacy analysis

The significance of the studied drug effect compared with Placebo will be tested by an Analysis of Covariance (ANCOVA) on the summary mean of ONLS at 12 and 15 months adjusted for baseline ONLS values. ANCOVA will be featured by a Linear Mixed Model (LMM), including baseline ONLS values and treatment as fixed factors, and center as random effect. The use of two repeated post-baseline measures increases the power to detect treatment differences in mean levels of the outcome measure over time (Frison and Pocock, 1992; Morgan and Case, 2013).

Two active doses will be compared to Placebo. As the monotonicity of dose effect is not assumed, each dose will be compared at a two-sided 2.5% significance level, in order to preserve an overall false-positive rate of 5%.

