Statistical considerations	
Analysis populations: The Full Analysis Set (FAS) will be constituted by all the randomized patients. The Per-Protocol (PP) population will include all the patients of the FAS without major protocol violation during the course of the study.
 
All the efficacy analyses will be conducted on the FAS population and reproduced on the PP population for sensitivity purposes. The safety analyses will be conducted on the FAS, given that all randomized patients will receive at least one dose of treatment.
 
Primary efficacy analysis: The significance of the studied drug effect compared with Placebo will be tested by an Analysis of Covariance (ANCOVA) on the summary mean of ONLS at 12 and 15 months adjusted for baseline ONLS values. ANCOVA will be featured by a Linear Mixed Model (LMM), including baseline ONLS values and treatment as fixed factors, and center as random effect.
 
Two active doses will be compared to Placebo. As the monotonicity of dose effect is not assumed, each dose will be compared at a two-sided 2.5% significance level, in order to preserve an overall false-positive rate of 5%.
 
Sample size calculation: Assuming ANCOVA with 2 post-baseline measures, a linear correlation coefficient of ONLS of $R = 0.75$ between baseline and end of the study, a standard deviation of ONLS of $SD \cong 1$, a standardized mean difference of $SMD = 0.3$ should be detected versus Placebo with a power of 90% at a two-sided 2.5% significance level when the sample size reaches at least 89 patients per group. Assuming a drop-out rate of $\cong 10\%$, we anticipate recruiting 100 patients per group for a total of at least 300 patients.
 
Secondary efficacy analyses: The primary ANCOVA analysis based on the summary mean at 12 and 15 months will be repeated on the other quantitative efficacy endpoints (see above). The significance of the treatment effect on each quantitative endpoint will also be evaluated based on the difference compared to Placebo in change from baseline at each individual visit and in slope of progression over the duration of the study. The proportion of responders at 15 months will be assessed through a Generalized Linear Mixed Model (GLMM) featuring logistic regression, and admitting center as a random effect.
 
Missing data: Missing values will be imputed using a linear model estimated on the Placebo group. The potential impact of missing data on the study's conclusions will be evaluated.
 
Safety analyses: Safety and tolerability will be assessed by summarizing and analyzing adverse events (AEs), change in physical examination, vital signs, electrocardiogram (ECG) and laboratory data.
 
Data Safety Monitoring Board (DSMB): An independent DSMB will regularly follow the progress of the clinical trial, monitor safety data and critical efficacy variables, and be consulted concerning the opportunity of modifying the sample size or terminate the trial for futility.
 
Adaptive sample size: An estimation of the adjusted standard deviation (ASD) will be performed when 80 patients are available. In case where the absolute value of the difference between the observed ASD and the value used for initial sample size calculation

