The walking tests are expected to be partly correlated with ONLS, CMTNS and QMT. However, in the previous clinical trials, 6-Minutes Walking Test (6-MWT) was used, but a clear training effect was shown along the successive visits in all groups, with no difference with the placebo group so that finally it does not seem to be relevant to evaluate CMT disease. The 6-MWT is time consuming and requires a large space to be practiced.

Better than an endurance test on a long distance, most of the interviewed experts prefer to test the speed to walk on a small distance as the limited dorsiflexion in CMT induces walk impairment particularly at start. The time to walk 10 meters is proposed.

The 10m WT is simple to administer, standardized, reliable and valid evaluation of functional exercise capacity and gait that has been proven reliable in neurologic disorders (Watson, 2002; Tyson and Connell, 2009) and in CMT patients (Solari, Laura *et al.*, 2008). Results recorded are the time to walk 10 meters and the number of steps performed.

Even if walk tests have been proven reliable in other pathologies including neurologic disorders, their reliability and sensitivity are not established in CMT and need to be assessed. The walking test is sensitive to fatigue related changes and to ankle status (walk ability may be modified if orthese or surgery) and it correlates with established outcome measures. However it only reflects the ability to walk 10 metres in a controlled environment at a constant speed. The walking test is expected to be partly correlated with ONLS, CMTNS and QMT.

F. Electrophysiological parameters

Sensory and motor responses measured at ulnar and radial nerves on the non-dominant side:

- Compound Muscle Action Potential (CMAP) on ulnar nerve
- Sensory Nerve Action Potential (SNAP) on radial nerve
- Nerve Conduction Velocity (NCV)

For CMT, it is usual to measure motor and sensory amplitudes of one nerve (ulnar is recommended for CMAP and radial for SNAP in the modified CMTNS version 2).

CMAP appears as weakly reliable since affected by the positioning of the electrodes and hence is physician-dependent. NCV is a more reliable measure since relatively unaffected by the electrodes positioning and is only affected by the skin temperature.

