14.3 Sample size calculation

Assuming ANCOVA with 2 post-baseline measures, a linear correlation coefficient of ONLS of $R = 0.75$ between baseline and end of the study, a standard deviation of ONLS of $SD \approx 1$, and a negligible between center standard deviation (estimated $SD = 0.13$ [0;0.35]), the resulting adjusted standard deviation $ASD \approx [1*(1-.75^2)]^{.5} \approx 0.65$, thus a minimum clinically relevant difference in ONLS should be a Cohen's Δ of $0.65/2 \approx 0.325$, rounded to $\Delta = 0.3$. From calculations based on compound symmetry of the covariance matrix (Frison and Pocock, 1992, Morgan and Case, 2013), such a difference should be detected versus Placebo with a power of 90% at a two-sided 2.5% significance level when the sample size reaches at least 89 patients per group. Assuming a drop-out rate of $\approx 10\%$, we anticipate recruiting 100 patients per group for a total of at least 300 patients.

The parameters needed for sample size calculation were evaluated based on historical trials (Micallef, Attarian *et al.*, 2009; Pareyson, Reilly *et al.*, 2011; Attarian, Vallat *et al.*, 2014).

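### The primary ONLS model adjusts for one baseline ONLS reading only; prespecifying baseline CMTNS-v2, already collected on every eligible patient, is an optional and probably small precision gain

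*Combined protocol and SAP*

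**What the plan says.** Section 14.2 analyses the "summary mean of ONLS at 12 and 15 months adjusted for baseline ONLS values". The model is described as "including baseline ONLS values and treatment as fixed factors, and center as random effect". The synopsis gives the same terms, and neither place names another baseline covariate.

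Section 14.3 sizes the trial with "a linear correlation coefficient of ONLS of $R = 0.75$ between baseline and end of the study" and a standard deviation of about 1, and finds a difference of 0.3 detectable "with a power of 90% at a two-sided 2.5% significance level when the sample size reaches at least 89 patients per group".

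ONLS is a sum of integer grades from 0 to 12 (section 8.4.1.3 A and Appendix 2). The flow chart in section 3 schedules one pre-treatment ONLS, at V1. CMTNS-v2 is an entry criterion (section 9.1, score above 2 and at most 18). It is scored at V0 and again at V1 before randomization (sections 3 and 11.2.2), and screening electrophysiology may be reused at V1 if it is no more than 14 days old. The protocol gives no reason for leaving CMTNS-v2 out of the model. Section 14.9 defers further detail to a SAP, and no separate SAP text is in the file.

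**The concern.** One reading on a coarse scale is an imperfect measure of a patient's stable severity. With R = 0.75, baseline ONLS leaves part of that stable level in the residual, where it widens the confidence interval. A second baseline severity score could recover some of it. CMTNS-v2 is a natural candidate: its items on buttons, walking aids and wheelchair use cover the same ground as ONLS items (Appendices 2 and 3). It is measured before treatment, so adjusting for it introduces no post-randomization bias, and it needs no new data. What is at stake is a modest amount of precision in each comparison of a dose with placebo, not the validity of the test.

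**Working it through.** **Inputs from section 14.3.** ONLS SD about 1; R = 0.75; two post-baseline measures under compound symmetry; difference 0.3; two-sided alpha 0.025 per dose; power 90%; 89 per group. Center is ignored, because the plan calls its variance negligible.

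**Step 1: reproduce the plan's figure.**
- Variance of the mean of two post-baseline measures: (1 + 0.75)/2 = 0.875.
- Explained by baseline ONLS: 0.75² = 0.5625.
- Residual variance: 0.875 − 0.5625 = 0.3125 (SD 0.559).
- n per group = 2 × 0.3125 × (2.2414 + 1.2816)² / 0.3² = 86.2, so 87. The noncentral-t version gives 88. The stated 89 is reproduced.
- With a single post-baseline measure (SD 0.661) the answer would be 121, so the two-measure variance is the one behind the 89.
- Power at 89 per group: 0.3/√(2 × 0.3125/89) = 3.580, and Φ(3.580 − 2.2414) = 91.0%.

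**Step 2: how much of the residual another baseline measure could reach.** Under compound symmetry the stable between-patient variance is 0.75. Baseline ONLS removes 0.5625 and leaves 0.1875. Visit-level noise in the two-visit mean is 0.25/2 = 0.125. So 0.1875/0.3125 = 60% of the residual is in principle explainable by other baseline information.

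**Step 3: add baseline CMTNS-v2.** Let r_base and r_post be its correlations with baseline ONLS and with ONLS at each follow-up visit. Neither is in the documents; both are assumptions. The additional variance explained is

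(r_post − 0.75 × r_base)² / (1 − r_base²).

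With a common r at every visit this becomes 0.0625r²/(1 − r²):

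| r | Extra variance explained | Residual variance | Reduction | Power at 89 per group |
|---|---|---|---|---|
| none | 0 | 0.3125 | 0 | 91.0% |
| 0.3 | 0.0062 | 0.3063 | 2.0% | 91.5% |
| 0.4 | 0.0119 | 0.3006 | 3.8% | 92.1% |
| 0.5 | 0.0208 | 0.2917 | 6.7% | 92.8% |
| 0.6 | 0.0352 | 0.2773 | 11.3% | 94.0% |

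A simulation at r = 0.5 agrees: residual variance falls from 0.312 to 0.291.

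**Step 4: relax the common correlation.** Hold r_base at 0.5, so that 0.75 × r_base = 0.375 and 1 − r_base² = 0.75:

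| r_post | Extra variance explained | Reduction |
|---|---|---|
| 0.50 | 0.125²/0.75 = 0.0208 | 6.7% |
| 0.45 | 0.075²/0.75 = 0.0075 | 2.4% |
| 0.40 | 0.025²/0.75 = 0.0008 | 0.3% |
| 0.375 | 0 | 0% |

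A fall of 0.05 in the follow-up correlation removes about two thirds of the gain, and a fall of 0.125 removes all of it.

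**The case against.** The plan is coherent as written. ANCOVA on the endpoint's own baseline with two post-baseline measures is a recognised choice, and it reaches its power target without CMTNS-v2. That stands.

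Three stronger readings are tempting, and the documents do not support them.

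- A reader might infer that precision is demonstrably being lost. That depends on an unreported correlation. Section 8.4.1.3 E says "The walking tests are expected to be partly correlated with ONLS, CMTNS and QMT", but this concerns walking tests and does not show that baseline CMTNS-v2 predicts later ONLS once baseline ONLS is in the model. There are also reasons for doubt. The entry range narrows CMTNS-v2; section 8.4.1.3 B describes floor and ceiling effects, subjective items and two electrophysiological components; and both scores are taken at V1, so shared same-visit error could make r_base larger than r_post.
- A reader might infer that the trial now rests on Dose 1 versus placebo alone. Section 14.2 still tests both doses, and the amendment sends the incomplete Dose 2 data to section 14.5.
- A reader might want the covariate in every secondary model. CMTNS-v2 total is itself a secondary endpoint, so there it would be entered twice. For its sub-items, CMAP and SNAP it contains or overlaps the endpoint's own baseline.

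It is also fair to say that changing the primary model late has a credibility cost, given that section 7 records EMA and FDA advice on the design. Finally, a separate SAP might already add covariates, and this cannot be checked. On the other side, the five-year observation in section 8.4.1.3 A that CMTNS did not move while ONLS rose concerns sensitivity to change. A covariate only has to predict level.

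**Conclusion.** The point holds as an optional efficiency gain limited to the primary ONLS model. It is not an error, and the trial is not underpowered on its own inputs. For a common correlation between 0.3 and 0.6, the gain is 2.0% to 11.3% of residual variance, or 0.5 to 3.0 points of power at 89 per group. These figures rest on the plan's SD, R and compound symmetry, on a normal approximation, and on an assumed correlation that is equal at baseline and follow-up. If the follow-up correlation is weaker, the gain may be negligible, and the cost is then about one degree of freedom. A small gain is likely because the item content overlaps and the single baseline ONLS reading is noisy, but its size is not established.

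**What to change.** Before the analysis is unblinded, state in the SAP that the primary ONLS model includes the baseline CMTNS-v2 total as one continuous covariate alongside baseline ONLS, treatment and center. Define baseline as the V1 score, using screening electrophysiology where the protocol allows it. Keep the model of section 14.2 as a sensitivity analysis, and name which of the two is primary.

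Section 14.4 repeats the primary ANCOVA on the other quantitative endpoints, so say explicitly that the covariate does not carry over to the models for CMTNS-v2 total, its sub-items, CMAP or SNAP.

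The cost is one line in the SAP, one degree of freedom, and notifying the agencies that advised on the protocol. No new visit or measurement is needed. If the sponsor prefers not to change the primary model at this stage, a sentence recording why CMTNS-v2 is left out would close the point.

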14.3 Sample size calculation

Assuming ANCOVA with 2 post-baseline measures, a linear correlation coefficient of ONLS of $R = 0.75$ between baseline and end of the study, a standard deviation of ONLS of $SD \approx 1$, and a negligible between center standard deviation (estimated $SD = 0.13$ [0;0.35]), the resulting adjusted standard deviation $ASD \approx [1*(1-.75^2)]^{.5} \approx 0.65$, thus a minimum clinically relevant difference in ONLS should be a Cohen's Δ of $0.65/2 \approx 0.325$, rounded to $\Delta = 0.3$. From calculations based on compound symmetry of the covariance matrix (Frison and Pocock, 1992, Morgan and Case, 2013), such a difference should be detected versus Placebo with a power of 90% at a two-sided 2.5% significance level when the sample size reaches at least 89 patients per group. Assuming a drop-out rate of $\approx 10\%$, we anticipate recruiting 100 patients per group for a total of at least 300 patients.

The parameters needed for sample size calculation were evaluated based on historical trials (Micallef, Attarian *et al.*, 2009; Pareyson, Reilly *et al.*, 2011; Attarian, Vallat *et al.*, 2014).

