Extension study, a DB 9-month Follow-up	
In order to stimulate the recruitment and motivate patients to be enrolled, patients having completed the 15-month study will be eligible to receive PXT3003 in a follow-up extension trial for 9 months if they are willing to continue the treatment. They will be attributed to active drug by a second randomization. This 9-month extension study will provide additional long-term data on safety and additional efficacy data that could provide some evidence of disease modifying effect.

Planned dates	
 - CTA & IND submission: from June 2015 - Start (First patient in): Q4 2015 - Patients recruitment: 1 year (end of recruitment: Q4 2016) - Study duration for each patient: 15-month double-blind period - Last patient out (ie., end of study): expected Q1 2018 in all the countries, except in Germany where the LPO is expected Q3 2018* - Clinical Study Report: expected Q2 2019 
* due to longer interruption of the study in Germany regarding the occurrence of crystals in the dose 2 IMP, the LPO in Germany is expected in Q3 2018

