14.8 Adaptive sample size

We based our sample size on the point estimates of the standard deviation (SD) and the correlation between baseline and final values (R). Over- or under- estimation is possible due to their wide spread variation. An estimation of the adjusted standard deviation ASD will be performed when 80 patients are available, producing a 95% half interval length of $ASD \pm 0.1$. In case where the absolute value of the difference between the observed ASD and the value used for initial sample size calculation exceeds 0.1, the sample size will be recalculated. In addition, the drop-out rate of 10% used for sample size calculation will be also updated if its estimation on the first 100 patients is significantly greater and non-related to safety concerns. The adaptive sample size calculation will be organized blind to treatment and do not require any type-I adjustment.

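### Section 14.3 prints a one-visit adjusted SD (0.65) beside a sample size that rests on the two-visit SD (0.56), and 14.8 does not say which of them its re-estimation trigger uses

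*Combined protocol and SAP*

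**What the plan says.** Section 14.3 takes an SD of ONLS of about 1, "a linear correlation coefficient of ONLS of $R = 0.75$ between baseline and end of the study", and two post-baseline measures. It gives "the resulting adjusted standard deviation" (ASD) as the square root of 1 − 0.75², printed as about 0.65, halves it to 0.325 and rounds that to a target difference of 0.3. It then turns to calculations under compound symmetry and reports detection "with a power of 90% at a two-sided 2.5% significance level when the sample size reaches at least 89 patients per group". The SD implied by that second calculation is not printed. Allowing for 10% drop-out, 14.3 plans 100 per group.

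Section 14.2 makes the primary variable the mean of ONLS at months 12 and 15, adjusted for baseline, and sets the error rate: "each dose will be compared at a two-sided 2.5% significance level, in order to preserve an overall false-positive rate of 5".

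Section 14.8 names SD and the baseline-to-final correlation as the uncertain inputs. It plans an estimate of the ASD at 80 patients, with a stated 95% half-width of 0.1, and recalculates when "the difference between the observed ASD and the value used for initial sample size calculation exceeds 0.1". It gives no number for that value and does not say whether the ASD is for one visit or for the two-visit mean. The Synopsis repeats the rule, and its planned dates give "Patients recruitment: 1 year (end of recruitment: Q4 2016".

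**The concern.** The only ASD printed in the plan is 0.65, and 14.3 introduces it as the result of a two-measure ANCOVA. It is a one-measure quantity. A reader who treats it as the SD behind the sample size cannot get back to 89 and would think the trial is powered at about 79%.

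The larger issue is 14.8, where the ASD becomes part of an operating rule. Two statisticians could apply the rule to the same blinded data, one using the 12/15-month mean and the other a single visit, and reach different decisions. At stake is whether the safeguard against a wrong variance assumption monitors the variance that determines the power of the primary test.

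**Working it through.** **Inputs.** From 14.2 and 14.3: difference 0.3 ONLS points, SD 1, R = 0.75, two post-baseline measures, compound symmetry (so the correlation between months 12 and 15 is also 0.75), two-sided 2.5%, power 90%. From 14.8: 80 patients, band 0.1. The centre effect is ignored, since 14.3 calls it negligible.

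**Adjusted SDs.**
- One visit: √(1 − 0.75²) = √0.4375 = 0.661 (printed as about 0.65).
- Mean of two visits: √[(1 + 0.75)/2 − 0.75²] = √(0.875 − 0.5625) = √0.3125 = 0.559.

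**Reproducing 89.** n = 2·SD²·(2.2414 + 1.2816)²/0.3², with power at 89 per group from the noncentral t:
- SD 0.559: n = 86.2, so 87 (88 with the t correction); power 90.5%. The stated 89 is reproduced to within two patients.
- SD 0.65: n = 116.5, so 117; power 79%.
- SD 0.661: n = 120.7, so 121; power 78%.

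Solving back from 89 gives an SD of 0.564 to 0.568. Using 0.65 with a difference of 0.325 gives 100; using it at two-sided 5% gives 99. Neither returns 89.

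**Trigger if the ASD is that of the 12/15-month mean, reference 0.65** (limits 0.55 and 0.75; chi-square with 77 df):
- True SD 0.559, exactly on plan: P(observed < 0.55) = 44%.
- True SD 0.70 (power 73% at 90 per group): P(observed > 0.75) = 18%.
- An observed 0.75 does not trigger; if true, power at 89 is 66% and 157 per group would be needed.

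These use a residual SD free of any treatment effect. A blinded SD would absorb some: if both doses gained 0.3, the added variance is (1/3)(2/3)(0.3²) = 0.02. The on-plan SD becomes √0.3325 = 0.577, and the 44% becomes about 30%. For a true 0.70 the blinded SD becomes √(0.49 + 0.02) = 0.714, and the 18% becomes about 25%.

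**Same variable, reference 0.56** (limits 0.46 and 0.66):
- On-plan 0.559 triggers 2.6% of the time, both directions together.
- True 0.70 triggers upward 75% of the time.
- True 0.66 (power 78% at 89) triggers upward 48% of the time; true 0.60 (power 86%) only 10%.

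**Trigger if the ASD is the one-visit SD, reference 0.65.** A true 0.661 triggers 1.8% downward plus 4.6% upward, about 6%. But the variance of the primary variable is (1 + r)/2 − 0.5625, where r is the correlation between months 12 and 15, and r does not enter the one-visit SD. With the one-visit SD held at 0.661, power at 90 per group is:
- r = 0.75: SD 0.559, power 91%.
- r = 0.95: SD 0.642, power 81%.

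The documents give no value for r apart from compound symmetry; 0.75 to 0.95 is an assumed range.

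**Timing.** With 300 patients over 12 months at a uniform rate (an assumption), the 80th enters at 80/300 × 12 = month 3.2. Month-12 data on 80 patients are complete at about month 15.2 and month-15 data at about 18.2, both after planned enrolment ends.

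**The case against.** The best defence is that 14.3 and 14.8 are consistent on the one-visit scale. Section 14.3 defines the ASD by the one-visit formula; 14.8 speaks of the correlation between baseline and final values; and its half-width of 0.1 fits 0.65 (1.96 × 0.65/√158 = 0.101) better than 0.56 (0.087). Read this way, the reference is like-for-like and false triggers are about 6%. This stands, and it is the reading the wording favours. So the 44%, 18% and 66% figures apply only under the alternative reading.

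A reader might also infer that 89 is wrong, or that the trial has only 79% power by design. The documents do not support that. Section 14.3 uses 0.65 to set the difference, never says it entered the formula for n, and attributes n to compound symmetry, which reproduces 89. Nor can it be said flatly that 14.8 uses a wrong reference, since it names no number. A downward trigger would lead to a recalculation, not an automatic cut: 14.7 has the DSMB consulted on any change, and the target is at least 300 patients.

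It is also fair that correcting the reference does not restore 90% power, because the 0.1 band leaves a gap of its own. And this protocol version is dated December 2017, after the planned end of recruitment, so rewording 14.8 is unlikely to change enrolment.

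What survives is that the printed ASD does not match the two-measure basis stated for it, and that neither reading of 14.8 gives a sound check on the primary variance.

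**Conclusion.** The point holds as a mislabelled SD and an undefined monitoring quantity, not as a sample size error. The SD behind 89 per group is 0.559; the printed 0.65 is the one-visit value, loosely rounded from 0.661. Applied to the primary variable, a reference of 0.65 is about 0.09 too high and shifts the trigger in the unsafe direction: likely to act when the design is on plan, unlikely to act when power has fallen to 73%. Applied to one visit, the reference is right but the check misses one of the quantities that drive power, worth up to about ten percentage points over the assumed correlation range. Under either reading, and also after correction, the rule does not guarantee 90% power. The figures assume a difference of 0.3, 89 or 90 evaluable patients per group as stated, a negligible centre effect and 77 residual df.

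**What to change.** - **14.3:** state 0.56 as the SD of the two-visit mean given baseline that gives 89 per group, and label 0.66 as the one-visit value.
- **14.8 and Synopsis:** define the ASD as the blinded residual SD of the 12/15-month mean given baseline, with reference 0.56, and recalculate or restate power from that same SD. This captures the correlation between months 12 and 15 directly.
- **Band:** either state that an observed SD of 0.66 (about 78% power at 89) passes untriggered, so the rule does not guarantee 90% power, or drop the band and report the updated power whatever the difference.
- **Timing:** say that under the planned one-year recruitment, 12/15-month data on 80 patients arrive after enrolment ends, so the check updates only the reported power. Moving it to month-6 data would not help, because those cannot estimate a 12/15-month SD.

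The cost is a few lines of wording and one blinded SD estimate. The drawback is that the check is openly described as one that cannot enlarge the trial on the planned timeline.
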